E.2.3. Secondary objective #2. The primary endpoint will be the baseline to day 7 difference in dyspnea NRS (>1.0 is considered clinically significant). We will use logistic regression analysis to identify independent predictors of this outcome, including baseline dyspnea NRS, restrictive or obstructive lung disease pattern, MIP, sex, and baseline inflammatory cytokine levels (IL-1 β , IL-6, IL-8, IL-10, and TNF- α). We will plot the data and use residual analyses to verify assumptions of the model and take appropriate actions if they appear to be validated (e.g., transforming the data). We will use the variance inflation factor to identify collinearity. With 116 dexamethasone-treated patients, we would have at least 80% power to detect an odds ratio of 2.5 (for a one-unit change in a normally distributed marker) if the response probability is at least 30% (assuming 5% alpha and a correlation between the marker and the other factors in the model of 0.30). As an exploratory analysis, we will perform a similar analysis to that described for the primary endpoint to determine whether patients achieved their personal goal in dyspnea improvement. We will perform a similar exploratory linear regression analysis using

the difference between the day 7 and baseline dyspnea NRS scores as the endpoint. Additional exploratory correlative analyses will be conducted for changes in inflammatory markers between day 7 and baseline.

E.2.4. Secondary objective #3. We will calculate summary statistics for duration of dexamethasone dosing and cumulative dexamethasone dose. Two-sample t-tests or Wilcoxon rank sums tests will be used to examine whether binary events, such as adverse events, are associated with higher doses or duration of dexamethasone. If number of hospital admissions follows a Poisson distribution or zero-inflated Poisson distribution, we will use the appropriate model to examine the association of number of hospitalizations with cumulative dose and duration. All patients, regardless whether they received placebo, will be used to examine dose and duration initially. In these analyses, dose and duration for patients who received placebo will be set to zero. In a second set of analyses, only those patients who received dexamethasone will be included in the analyses. All testing will be 2-sided with 5% alpha. We will consider limiting the false detection rate to 10%.

E.2.5. Secondary objective #4. We will tabulate agreement between CTCAE adverse events and adverse events collected from the PRO-CTCAE form. We will also conduct chi-squared testing or Fisher's exact tests to determine whether treatment assignment or any other potential factors affects agreement. All testing will be 2-sided with 5% alpha. We will consider limiting the false detection rate to 10%.

E.2.6 Open label phase: We will conduct descriptive analyses to summarize the findings in the open-label phase in each arm. Exploratory analyses, as appropriate, will also be conducted to examine the between-group difference for various outcomes for hypothesis-generating purposes only.

E.2.7. Interim analysis: We will conduct two interim analyses (when roughly 33% and 67% of patients have been enrolled). We will look at both superiority (efficacy) and futility using O'Brien-Fleming boundaries. For futility, the p-value boundaries are 0.980, 0.359, and 0.046. For superiority, the Z-value boundaries are +/- 3.710, +/- 2.511, +/- 1.993. Calculations were done in East 6.

F. Data Confidentiality Procedures

Health information will be protected and we will maintain the confidentiality of the data obtained from the patient's chart to the best of our ability.

Collection of identifiers: We will collect and securely store patients' identifiers (including name, medical record number, and date of birth). Each patient will be assigned a study number that will be the only identifier to figure in the analytical file and personal data will not be disclosed in any form. The key linking these numbers will be retained in a securely locked file by the investigator.

Data Storage: Protection of electronic and paper records will be maintained to the best of our ability. All electronic records will be stored on password-protected institution computers behind the institution firewall. Any paper records will be classified and stored in locked files inside a locked office.

Training of personnel: Only MDACC personnel trained in maintaining confidentiality, the principal investigator, co-investigators, and research staff will have access to study records.

Data sharing: Study data will not be shared with any individuals or entities without an IRB-approved protocol.

Final disposition of study records: PHI may be maintained indefinitely, aggregated in the future, and used for future IRB-approved research studies.

G. References

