We will keep track of adherence by pill count. Patients will receive daily phone calls or other remote contact for reminders and assessments. They can take it as soon as possible if they forget a dose.

D.6. Blinding. Both patients and the research staff conducting the assessment will be blinded to the treatment assignment. Placebo capsules identical to dexamethasone 4mg capsules in appearance and taste will be manufactured by a compounding pharmacy, and both will be dispensed by Investigation Pharmacy at MD Anderson. At the end of the blinded phase, we will assess blinding by asking patients which study arm they believe they have been randomized to.

To minimize bias during statistical analyses, we will also blind the biostatisticians to the group assignment (groups A/B instead of dexamethasone/placebo) until they have completed the analyses pre-specified in the statistical analysis section after completion of study enrollment.

D.7. Study assessments. See Table 3 for a detailed description of study assessments. Study assessments will be conducted either in-person, by phone, or other remote methods as previously detailed (vetted platforms consisting of WebEx, Skype, FaceTime, or Zoom) during the course of the study.

D.7.1. Baseline characteristics. We will collect the following information to characterize the study population: date of birth, sex, race, education, marital status, cancer diagnosis, comorbidities, cause(s) of dyspnea, medications (e.g., scheduled and as-needed opioids, bronchodilators), and Karnofsky Performance Status (Schag *et al.* 1984).

D.7.2. Dyspnea NRS. The dyspnea NRS score will be the primary study outcome measure. The dyspnea NRS is an 11-point categorical scale validated for rating the average intensity of dyspnea over the past 24 hours, ranging from 0 (no dyspnea) to 10 (worst dyspnea) (Dorman *et al.* 2007, Gift and Narsavage 1998, Powers and Bennett 1999). It has been extensively validated and translated into multiple languages, including Spanish (Carvajal *et al.* 2011, Chang *et al.* 2000, Moro *et al.* 2006, Nikolaichuk *et al.* 2008, Paiva *et al.* 2015, Rees *et al.* 1998, Richardson and Jones 2009, Vignaroli *et al.* 2006, Watanabe *et al.* 2012, Zeng *et al.* 2011). Dyspnea NRS

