score was chosen as the primary outcome measure instead of the modified Borg scale score because the dyspnea NRS was more responsive to change in our preliminary study (Hui *et al.* 2016a). Specifically, the dyspnea NRS has good discriminatory performance, with area under the receiver-operating characteristic curve of 0.71 for improvement and 0.79 for deterioration (Hui *et al.* 2015b). The MCID was 1 point for improvement and 1 point for deterioration (Hui *et al.* 2015b). In addition to intensity, we will assess the affective component (unpleasantness associated with dyspnea) using the same scale as one of the secondary measures.

D.7.3. Personalized dyspnea goal and personalized dyspnea response. The personalized dyspnea goal is determined by asking the patient, “At what level of shortness of breath intensity would you feel comfortable?” Personalized dyspnea response is defined as dyspnea NRS score \leq personalized dyspnea goal. Thus, personalized dyspnea response provides a simple yet individualized therapeutic “target” and allows for intra-patient determination of a symptom response that is both practical and meaningful (Section D.2.1.1). However, because personalized dyspnea goal has never been tested in randomized, controlled trials, we will consider personalized dyspnea response only as a secondary outcome.

D.7.4. Unpleasantness associated with dyspnea. We will ensure that each patient understands the differences between intensity and unpleasantness of breathlessness by providing clear instructions as follows: “Intensity refers to the pure level or magnitude of the sensation. It is like a physical measure: for example, ‘how much do you weigh in pounds?’ Intensity does not contain any pleasantness or unpleasantness, like or dislike, or measure of how terrifying the experience is to you. Unpleasantness describes how much you like or dislike something or feel terrified by it. High unpleasantness indicates that your breathing feels very bad or terrifying regardless of whether the intensity is high or low.”

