| Physiologic measures (i.e., spirometry, vital signs, maximal inspiratory pressure [MIP]; 20min) ⁴ (Appendix J) | ✓ | | ✓ | | ✓ | |
| Edmonton Symptom Assessment System (<3min) ⁵ (Appendix E) | ✓ | | ✓ | | ✓ | |
| HADS (<5min) ⁶ (Appendix H) | ✓ | | ✓ | | ✓ | |
| EORTC Quality of Life Questionnaire (QLQ)-C30 (<10min) ⁷ (Appendix F) | ✓ | | ✓ | | ✓ | |
| Adverse effects (10min) ⁸ (Appendix K) | ✓ | | ✓ | | ✓ | ✓ |
| Global assessment (<1min) ⁹ (Appendix G) | | | ✓ | | ✓ | |
| Pill count and check of blinding (<1min) ¹⁰ (Appendix L) | | | ✓ | | ✓ | |

¹The dyspnea NRS is a categorical scale ranging from 0 (no dyspnea) to 10 (worst dyspnea), validated for rating the average intensity of dyspnea over the past 24 hours (Dorman *et al.* 2007, Gift and Narsavage 1998, Powers and Bennett 1999). It is part of the ESAS (Bruera *et al.* 1989). The MCID is 1 point (Hui *et al.* 2015b). We will ask patients to rate the unpleasantness of dyspnea over the past 24 hours as well using the same NRS (i.e., ranging from 0 to 10).

²We will assess personalized dyspnea goals for dyspnea intensity by asking “At what level of intensity would you feel comfortable, on a scale of 0 to 10 where 0 = no shortness of breath and 10 = worst possible?” (Hui *et al.* 2016b). As an exploratory measure, we will also assess the personalized dyspnea goal for unpleasantness related to dyspnea: “At what level of unpleasantness would you feel comfortable, on a scale of 0 to 10 where 0 = no unpleasantness related to shortness of breath and 10 = worst possible?” Personalized dyspnea response is defined as dyspnea NRS ≤ personalized dyspnea goal. To assess the stability of personalized dyspnea goals, we will ask participants to provide this on day 14 ± 2 as well.

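### The responder cut-off in E.2.3 (strictly above 1.0 on a whole-number scale) requires a 2-point change, inconsistent with the plan's own 1-point MCID

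*Combined protocol and SAP*

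**What the plan says.** Section E.2.3 sets the endpoint for the predictor analysis: "The primary endpoint will be the baseline to day 7 difference in dyspnea NRS (>1.0 is considered clinically significant". The dichotomy is then modelled: "We will use logistic regression analysis to identify independent predictors of this outcome". The power sentence reads "With 116 dexamethasone-treated patients, we would have at least 80% power to detect an odds ratio of 2.5", on the condition "if the response probability is at least 30" percent.

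Three other statements bear on the cut-off:

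- Section D.7.2, on the scale: "The dyspnea NRS is an 11-point categorical scale", running from 0 to 10.
- Section D.7.2, on the smallest important change: "The MCID was 1 point for improvement and 1 point for deterioration".
- Table 3, footnote 1, on the same quantity: "The MCID is 1 point".

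E.2.3 also lists an exploratory linear regression on the change score and an exploratory analysis of whether patients reached their personal goal. The primary analysis in E.2.1 compares day 7 scores as a continuous outcome.

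**The concern.** A responder definition tied to clinical significance should agree with the minimal important difference that the same document adopts. Here the strict inequality doubles it: on whole-number scores, the smallest improvement that counts is 2 points.

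Patients who gain exactly 1 point meet the MCID in D.7.2 and fail the rule in E.2.3. Two analysts, one following the MCID and the other the inequality, would fit different outcome variables to the same data. This is the named main endpoint of secondary objective #2, and section D.1.8 gives that objective as one reason for the 2:1 allocation. The cut-off should be settled before the data are seen.

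**Working it through.** **1. What the cut-off means.** Baseline and day 7 scores are integers from 0 to 10, so their difference is an integer. Listing every pair of baseline 4-10 and day 7 score 0-10, the smallest improvement above 1.0 is 2, and the smallest that is at least 1 is 1. The two rules differ only for patients who improve by exactly 1 point.

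**2. The plan's power figure.** For logistic regression with one normal covariate, the Hsieh-Bloch-Larsen formula is

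n = (z₀.₉₇₅ + z₀.₈₀)² / [p(1−p)(ln OR)²] / (1−R²).

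Inputs from E.2.3 are OR 2.5, p = 0.30, 5% alpha (taken as two-sided, as in E.1) and a correlation of 0.30. That correlation gives R² = 0.09 if it is R; R² = 0.30 is the harsher reading. With (1.960 + 0.842)² = 7.85 and (ln 2.5)² = 0.840:

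- R² = 0.09: n = 7.85 / (0.21 × 0.840) / 0.91 ≈ 49; power at 116 is 99.1%.
- R² = 0.30: n = 7.85 / (0.21 × 0.840) / 0.70 ≈ 64; power at 116 is 96.6%.

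Simulation of the adjusted Wald test (2,000 runs) gives 97% and 92%. The older and more conservative Hsieh formula needs 94 and 122 patients, so only its harsher case slightly exceeds 116. The plan's claim of at least 80% reproduces as a lower bound.

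**3. How many patients are affected (illustration).** The pilot results in section C.3 and its table give a day 7 change on dexamethasone of -1.8, 95% CI -3.2 to -0.3, N = 16. The implied SD of change is (2.9/2) × √16 / 2.131 ≈ 2.7. I treat change as normal and rounded to whole points, with SD from 2.0 (E.1's planning value) to 3.0:

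- P(improve by at least 1) = Φ[(−0.5 + 1.8)/SD]
- P(improve by at least 2) = Φ[(−1.5 + 1.8)/SD]

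| SD | At least 1 | At least 2 (the strict rule) | Exactly 1 | Of 116 |
|---|---|---|---|---|
| 2.0 | 74.2% | 56.0% | 18.3% | 21 |
| 2.7 | 68.4% | 54.4% | 14.0% | 16 |
| 3.0 | 66.8% | 54.0% | 12.8% | 15 |

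(The 2.7 row uses the unrounded 2.72.)

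**4. Power under either rule.** The condition is a response probability of at least 30%. Every rate in the table exceeds it. At 116 patients the formula in step 2 gives 98.4-99.7% at p = 0.54 and 97.1-99.2% at p = 0.68; simulation gives 96-99% and 94-97%.

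**The case against.** The best defence is that an MCID is a minimum. A responder definition may sit above it, and E.2.3 does not cite the MCID by name. A stricter bar could be deliberate. That possibility stands, and the fix allows for it. But the plan writes 1.0, the same value as its MCID, gives clinical significance as the only rationale, and offers no reason for 2 points.

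The size is also only illustrative. It rests on rounded confidence limits from 16 pilot patients, whose dexamethasone schedule differed from this trial's on days 5-7 (C.3 against D.5). That stands too, hence the range.

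A reader might infer more than the documents support:

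- **That the rule discards the most common meaningful change.** In the dexamethasone arm, under the same model, a 2-point improvement is slightly more frequent than a 1-point one (14.5% against 14.0% at SD 2.72).
- **That it blurs marker associations.** Nothing here shows this. Under the same model the strict rule splits the arm nearer its median, which gives no support for a loss of information.
- **That it upsets the power statement.** The 30% floor holds under both rules.
- **That worsening could count as response.** The difference is unsigned, but the objective and the rest of E.2.3 speak of response and improvement, so the intent is clear. Stating the sign is tidying.

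The exploratory regression on the change score needs no cut-off. It softens the problem, but being exploratory it does not replace the named endpoint.

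**Conclusion.** The inconsistency holds. Followed as written, E.2.3 codes as non-responders patients who reach the MCID given in D.7.2 and Table 3. The step from above 1.0 to at least 2 needs only whole-number scores. The size needs the assumptions of a normal change, the pilot mean of -1.8 and an SD of 2.0-3.0: about 13-18% of the dexamethasone arm (15-21 of 116) change class, and the responder rate is 54-56% rather than 67-74%.

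The consequence is confined to the responder analysis of secondary objective #2. The primary comparison and the power claim stand. It should be corrected, but it does not threaten the trial's main conclusion.

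**What to change.** In E.2.3, define response as baseline minus day 7 dyspnea NRS of at least 1, which matches the stated MCID and fixes the direction as improvement. If a 2-point threshold is intended, write at least 2, give the reason, and report the 1-point (MCID) definition as a sensitivity analysis.

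The cost is one symbol and one clause, plus one additional model if the 2-point threshold is kept. Sample size, data collection and the power sentence need no change.

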A Randomized Controlled Trial of Dexamethasone for Dyspnea in Cancer Patients

Principal investigator: [name]

Co-investigators: [name], [name], [name], [name]

Biostatistics Collaborators: [name]; [name], PhD; [name], MS

Table of Contents

| | |
|------------------------------------|----|
| A. Objectives | 2 |
| B. Background | 2 |
| C. Rationale | 4 |
| D. Experimental Approach | 6 |
| E. Statistical Analysis | 14 |
| F. Data Confidentiality Procedures | 15 |
| G. References | 16 |

This study proposal was submitted the National Institutes of Health and received a score of 12 (i.e. top 2 percentile). National Cancer Institute is considering it for funding.

A. Objectives

Primary Objective: Compare the intensity of dyspnea (numeric rating scale [NRS]) in the dexamethasone arm with that in the placebo arm at week 1.

Our working hypothesis is that dexamethasone will improve dyspnea compared with placebo in patients with cancer.

Secondary Objective #1: Compare the effects of dexamethasone with those of placebo in terms of personalized dyspnea response (based on a personalized dyspnea goal), unpleasantness of dyspnea, other symptoms, health-related quality of life, respiratory physiologic function, and adverse effects at week 1 and week 2, as well as the intensity of dyspnea at week 2.

Our working hypothesis is that short-term, high-dose dexamethasone will improve personalized dyspnea response, unpleasantness of dyspnea, symptom burden, health-related quality of life, and respiratory physiologic function, with limited adverse effects.

Secondary Objective #2: Identify predictive markers of dyspnea response to dexamethasone.

Our working hypothesis is that baseline inflammatory response (interleukin [IL]-1 β , IL-6, IL-8, IL-10, IL-6:IL-10 ratio, and tumor necrosis factor- α [TNF- α] levels) and certain patient characteristics (e.g., high baseline dyspnea and restrictive lung disease pattern) are associated with increased treatment response.

Secondary Objective #3: Determine the association between adverse event (AE) development (i.e. G3+ AEs, hospitalizations, specific adverse events) and the dose/duration of dexamethasone. *Our working hypothesis is that longer duration and higher dose is associated with greater AEs.*

Secondary Objective #4: Examine the similarities and differences between CTCAE and PRO-CTCAE reporting. *We will identify where CTCAE and PRO-CTCAE overlap and how they differ from each other.*

B. Background

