C.3. Dexamethasone for cancer-related dyspnea (Hui *et al.* 2016a). We recently completed a double-blind, randomized, controlled trial to examine the effect of dexamethasone on dyspnea. Cancer patients with dyspnea were randomized to receive either dexamethasone (8 mg twice daily for 4 days, then 4 mg twice daily for 3 days) or placebo for 7 days, followed by an open-label phase for 7 days. We documented the within-arm changes in dyspnea (according to the dyspnea NRS), spirometry measures, quality of life, and toxic effects. Forty-one patients were randomized and 35 (85%) completed the blinded phase. As shown in Table 2, dexamethasone was associated with a significant reduction in dyspnea by day 4 (average change in dyspnea NRS score -1.9, 95% confidence interval [CI] -3.3 to -0.5, P = 0.01) and by day 7 (average change in dyspnea NRS score -1.8, 95% CI -3.2 to -0.3, P = 0.02). In contrast, placebo was associated with an average change in dyspnea NRS score of -0.7 (95% CI -2.1 to 0.6, P = 0.38) by day 4 and -1.3 (95% CI -2.4 to -0.2, P = 0.03) by day 7. This preliminary study was not powered to detect the between-arm difference. Dexamethasone was well tolerated with no significant toxicities. This pilot study provided important preliminary data for the current proposed trial. First, it showed that a double-blind, randomized, controlled trial of dexamethasone was feasible, with a low attrition rate. We expect to be able to enroll patients and successfully complete the proposed trial because the eligibility criteria are similar. Second, the study showed that dexamethasone was associated with a rapid within-arm improvement in dyspnea and may potentially represent an improvement over the placebo arm. Third, the moderate effect size for a single-modality intervention is encouraging given that there are currently no FDA-approved therapies for dyspnea. Confirmation of the benefit of dexamethasone in the proposed study will pave the way for future studies examining combination therapies that may result in a greater effect size. Finally, dexamethasone, at a dose of 8 mg twice daily for 4 days, was well tolerated with no significant adverse effects; thus, it is reasonable to consider extending this same dose for a total of 7 days. Based on the findings from this preliminary study, we propose a larger confirmatory trial to definitively assess the efficacy of dexamethasone for dyspnea, with the potential to greatly improve patients' symptom burden, function, and quality of life.

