D.1.6. Open label phase. This will offer all patients the opportunity for a trial of the active agent, which may enhance the rate of recruitment. It will also allow us to taper the corticosteroid dose slowly and to explore longer-term use of corticosteroids beyond 2 weeks.

D.1.7. Placebo control. The use of placebo control is justified because definitive evidence to suggest that dexamethasone is superior to placebo remains lacking (i.e., clinical equipoise). Patients in either study arm will have access to other contemporary treatments if already scheduled (e.g., opioids, bronchodilators). Because the primary outcome measure is a patient-reported outcome, placebo control is essential. Indeed, our previous research studies have consistently shown that a placebo offers clinically significant benefits with minimal harm (Bruera *et al.* 1993, Bruera *et al.* 2007).

D.1.8. Randomization in 2:1 ratio. The 2:1 ratio was elected to maximize the number of patients available for response predictor analysis (Aim 2) and to help to improve our chances of recruitment. On the basis of our preliminary data favoring dexamethasone, we believe this ratio is justified.

D.1.9. Selection of putative predictive markers.

D.1.9.1 Inflammatory biomarkers. Dexamethasone is hypothesized to modulate the inflammatory response to help treat dyspnea. We have selected IL-1 β , IL-6, IL-8, IL-10, and TNF- α for their specific relevance to dyspnea on the basis of our literature review.

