D.1.9.2. Pulmonary function. A large proportion of patients with cancer have restrictive lung disease (Hui *et al.* 2016a). In the fibrotic interstitial lung disease setting, there is evidence to support the use of corticosteroids for dyspnea (Bajwah *et al.* 2013). Thus, restrictive lung disease may be a predictive marker. Cachexia, a common syndrome in patients with advanced cancer, is associated with decreased respiratory muscle function (Coats 2002, Remels *et al.* 2013, Roberts *et al.* 2013), which in turn may be associated with dyspnea (Chiu *et al.* 2004, Travers *et al.* 2008). Indeed, short-term corticosteroids have been reported to have a positive impact on muscle strength in patients with various inflammatory disorders (Manzur *et al.* 2008, Sunderkotter *et al.* 2016). Mechanistically, a positive association between dyspnea response to dexamethasone and pulmonary function (i.e., baseline or change) would suggest that the therapeutic effect of corticosteroids on dyspnea is mediated peripherally, and a lack of association may imply more a central effect.

D.1.9.3. Baseline dyspnea function. Studies from our group and others consistently demonstrated that a high baseline symptom score is associated with a greater likelihood of response to both active intervention and placebo (De La Cruz *et al.* 2010, Hui *et al.* 2015b). Thus, the randomization scheme will stratify by this variable. We will also adjust for this variable in our statistical analysis.

D.2. Eligibility criteria (Table 2). We designed these criteria to maximize the study's generalizability. We will be stratifying by baseline dyspnea intensity and study site. We also

considered stratifying by other factors such as pulmonary function and inflammatory markers, but no other factors have been consistently found to be predictive markers at this time in cancer patients.

| Table 2. Study eligibility criteria |
|---|
| Inclusion criteria |
| 1. Diagnosis of cancer |
| 2. Dyspnea with an average intensity ≥ 4 on the dyspnea NRS (range 0-10) over the past week |
| 3. Seen at an outpatient clinic at MD Anderson Cancer Center or LBJ Hospital General Oncology Clinic |
| 4. Able to communicate in English or Spanish |
| 5. Karnofsky performance status $\geq 30\%$ |
| 6. Age 18 years or older |
| Exclusion criteria |
| 1. Delirium (i.e., score >13 on the Memorial Delirium Assessment Scale; range 1-30) |
| 2. Oxygen saturation $<90\%$ despite supplemental oxygen >6 L/minute |

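### Secondary Objective #2 seeks markers that predict response to dexamethasone, but the E.2.3 model has no placebo contrast or marker-by-treatment interaction, so it finds markers of improvement, not of drug benefit

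*Combined protocol and SAP*

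**What the plan says.** Section A gives Secondary Objective #2 as "Identify predictive markers of dyspnea response to dexamethasone". Its working hypothesis names baseline cytokines, high baseline dyspnea and a restrictive lung pattern as markers of a larger treatment response.

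E.2.3 takes an NRS change of more than 1.0 from baseline to day 7 as the clinically significant outcome and continues: "We will use logistic regression analysis to identify independent predictors of this outcome, including baseline dyspnea NRS", then lists lung disease pattern, maximal inspiratory pressure (MIP), sex and five cytokines. The analysis set is not stated. Two places imply the dexamethasone arm alone: the E.2.3 power statement is for 116 dexamethasone patients, and D.1.8 justifies 2:1 allocation partly by the numbers it provides for the Aim 2 predictor analysis. Treatment arm is not among the listed covariates. No marker-by-treatment term is planned in E.2.3 or anywhere else. E.2.3 calls its personal-goal, linear-regression and cytokine-change analyses exploratory, but not the main logistic model.

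Four other places bear on the point:

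- D.1.9.3 says that "a high baseline symptom score is associated with a greater likelihood of response to both active intervention and placebo".
- D.1.7 says that "a placebo offers clinically significant benefits with minimal harm".
- C.3 reports the pilot placebo change as -0.7 by day 4 "and -1.3 (95% CI -2.4 to -0.2, P = 0.03) by day 7"; the dexamethasone change by day 7 was -1.8.
- D.1.9.2 says that a positive association between dyspnea response and pulmonary function "would suggest that the therapeutic effect of corticosteroids on dyspnea is mediated peripherally".

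**The concern.** A predictive marker is one for which the difference between drug and placebo changes with the marker's value. A model fitted within one arm contains no such difference. A marker can relate to improvement on dexamethasone because the drug works better in those patients. It can also do so because the same patients would have improved on placebo, through natural course or through regression to the mean. The protocol itself says that baseline dyspnea behaves in this second way, yet it also names high baseline dyspnea as a hypothesised marker of treatment response.

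Pooling both arms in the listed model would not help, since it would still have no interaction. Nor does stratifying or adjusting for baseline NRS, because neither creates a contrast between arms.

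Followed exactly, the plan could report a purely prognostic marker as predicting response to dexamethasone, and could read an association with lung function as evidence of how the drug works. Later trials might then select patients on a marker that says nothing about drug benefit.

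**Working it through.** **1. The plan's own power figure.** Inputs from E.2.3: n = 116, odds ratio (OR) 2.5 per unit of a normally distributed marker (one unit taken as 1 SD), response probability p = 0.30, 5% alpha (two-sided, as in E.1), correlation 0.30 with other factors, so R² = 0.09.

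- SE = sqrt(1/[116 × 0.30 × 0.70 × 0.91]) = 0.212.
- ln 2.5 / SE − 1.96 = 0.916/0.212 − 1.96 ≈ 2.35, so power is 99.1% (99.7% at p = 0.50).
- The more conservative Hsieh (1989) formula, inflated by 1/(1 − R²), gives 88.7%.

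The stated lower bound of 80% is therefore correct for a within-arm association.

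**2. What that power detects.** I simulated 116 + 58 patients (the E.1 evaluable numbers), with one covariate correlated 0.30 with the marker and 2,000 trials per scenario. The documents give no responder rates by arm, so dexamethasone/placebo rates of 30/20, 30/30 and 50/40% were assumed.

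| Truth about the marker | Flagged, dexamethasone-only model | Flagged, interaction test |
|---|---|---|
| Prognostic only (OR 2.5 in both arms) | 97–99% | about 4% |
| Predictive (OR 2.5 on drug, 1.0 on placebo) | 97–99% | 58–72% |

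The planned model cannot tell the two apart.

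**3. Baseline NRS, where the documents allow some calibration.** The baseline to day-7 correlation was back-calculated from the pilot table in C.3. The SD of change, from the 95% CIs, is 2.72 on dexamethasone (n = 16) and 1.91 on placebo (n = 14).

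- Dexamethasone: (2.1² + 2.6² − 2.72²)/(2 × 2.1 × 2.6) = 0.35; 95% CI about −0.18 to 0.72.
- Placebo: (1.5² + 2.1² − 1.91²)/(2 × 1.5 × 2.1) = 0.48; 95% CI about −0.07 to 0.81.

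The baseline SDs come from 19 patients per arm, so these values are approximate. Simulation settings: integer NRS 0–10; baseline mean 5, SD 2 before applying entry at 4 or more; day-7 mean 3.4, SD 2.4; response is a drop of more than 1; Wald test at 5%; **no drug effect**. The correlation was set among enrolled patients.

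| Correlation | Baseline NRS flagged, dexamethasone-only model |
|---|---|
| 0.35 | 72.6% |
| 0.48 | 43.2% |
| 0.60 | 17.3% |
| 0.70 | 5.5% |

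The interaction test flagged it in about 5% of trials. If dexamethasone instead helps every patient equally, by 0.5 or 1.0 point (1.0 is the E.1 target), no marker is predictive. The within-arm rates stay at about 72% (correlation 0.35) and 43% (0.48), and the interaction test at about 5%.

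**4. Power of the interaction test.** SE = sqrt(1/[116 p₁q₁ × 0.91] + 1/[58 p₀q₀ × 0.91]), for a ratio of odds ratios of 2.5. At 30/20%: SE = sqrt(0.0451 + 0.1184) = 0.404; 0.916/0.404 − 1.96 ≈ 0.31, so power is 62%.

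| Response, dexamethasone/placebo | Formula, 5% alpha | Simulated, 5% | Formula, alpha 0.0111 | Simulated, 0.0111 |
|---|---|---|---|---|
| 50/50% | 77.6% | 73.8% | 57.1% | 52.5% |
| 30/30% | 70.2% | 67.9% | 48.1% | 44.7% |
| 30/20% | 62.0% | 59.8% | 39.2% | 37.1% |

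Alpha 0.0111 = 0.10/9 is the strictest step of a 10% false-discovery limit over the nine factors listed in E.2.3.

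**The case against.** The strongest reply has four parts.

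**Only baseline NRS is shown to mislead, and D.1.9.3 already treats it as non-specific.** With baseline NRS in the model, as E.2.3 plans, a null marker correlated 0.30 with it was flagged in 5% of trials (12% and 9% unadjusted, at correlations 0.35 and 0.48). This stands: regression to the mean in NRS does not spread to the cytokines or lung function. They would mislead only if themselves prognostic, and the documents give no placebo-arm evidence on that. But the plan cannot rule it out for any marker.

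**The false-flag rates run from 6% to 73% on one poorly known correlation.** This also stands. The simulated enrolled population (mean 5.8, SD 1.5) also differs from the pilot arms (5.0, SD 2.1 and 4.7, SD 1.5). Using the pilot dexamethasone means and SDs directly raises the rates, to about 99% at 0.35 and 57% at 0.70. The direction holds; the size is a range.

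**The analysis set is inferred, and the covariate list is open-ended.** True, but no reading of the text supplies an interaction.

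**The objective is secondary and the mechanism wording is hedged.** True, and it limits the severity. However, the main logistic model carries no exploratory label, and the objective uses the word predictive.

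**Conclusion.** The concern holds. The E.2.3 model answers a different question from the one Secondary Objective #2 asks, whether it is fitted in the dexamethasone arm or in both arms pooled. Its stated power is correct, but only for association with improvement.

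The conceptual gap needs no assumptions. Its size does: for baseline NRS the false-flag rate depends on an imprecise correlation, and for the other markers on whether they are prognostic. In the pilot, mean improvement on placebo was 1.3/1.8 = 72% of that on dexamethasone. The between-arm difference there was -0.5 (95% CI -2.2 to 1.2), so this shows only that improvement without the drug is not negligible.

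This is worth correcting before analysis. It does not touch the primary endpoint, the primary analysis or safety.

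**What to change.** 1. Use all randomized patients who started study treatment, as in E.2.1.
2. For each marker, fit arm, marker and marker × arm, adjusted for baseline NRS. For baseline NRS itself, fit arm, baseline NRS and their product. Do this in the logistic model and in the linear regression on NRS change that E.2.3 already labels exploratory.
3. Report the interaction estimates with 95% CIs as exploratory. Call a marker predictive, or draw the D.1.9.2 inference about mechanism, only on interaction evidence.
4. The multivariable dexamethasone-only model, with its mutual adjustment and collinearity check, can stay if it is labelled as predictors of improvement among dexamethasone-treated patients and the 80% power is tied to that association. This relabelling alone is the minimum fix.
5. If interaction power is quoted, give it as a range with its assumptions: 62–78% by formula (60–74% simulated) for a ratio of odds ratios of 2.5 at 5% alpha. It falls to 39–57% (37–53% simulated) at the strictest false-discovery step. E.2.4 and E.2.5 say only that such a limit will be considered, and E.2.3 has none. Missing marker data would lower these figures.

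The cost is analysis wording and some extra models; Table 3 already schedules the markers and NRS for all patients. The downside is wide intervals and possibly no marker that can be called predictive.
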